9.2 Other Statistical Analyses

Statistical assessments/methods for safety, efficacy, PK/PD, and immunogenicity are found in Section 11 of the Core. In instances where the statistical analysis plan (SAP) might contradict the analyses specified in the Core, the SAP supersedes the Core.

Available data from Part A2 will be pooled with data from Part A by dose. In addition, efficacy data from Part A2 may be analyzed separately. The relationship between dose and safety/efficacy may be explored. Analyses by dose may be conducted for, but not limited to, the following endpoints: frequency of AEs of special interest, ORR, and percent reduction in tumor burden by dose. A generalized linear model may be used to adjust for covariates or to model the relationship. Because of the limited number of subjects, the above analyses will be conducted if data warrant.

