11.3. Efficacy Analysis

ORR is the primary efficacy endpoint. For solid tumors, response evaluation will be based on the RECIST criteria (v1.1) and ORR is defined as the proportion of subjects with complete response (CR) or partial response (PR) on two consecutive tumor assessments at least 4 weeks apart according to RECIST (RECIST v1.1). In addition, immune-related RECIST (irRECIST) criteria will also be used for Probody therapeutics that are likely to be immunostimulating. For lymphoma, objective response will be based on tumor-specific criteria.

The secondary efficacy endpoints include duration of response (DOR), TTR, progression-free survival (PFS), and overall survival (OS).

TTR is defined as the time from the date of the first dose of study drug to first documentation of objective tumor response. TTR is only calculated for subjects in the response-evaluable population who have a confirmed objective tumor response.

DOR is defined as the time from the first documentation of objective tumor response that is subsequently confirmed to the first documentation of objective disease progression or death due to any cause, whichever occurred first. DOR is only calculated for subjects in the response-evaluable population who have a confirmed objective tumor response. Subjects who neither progress nor die will be censored on the date of their last tumor assessment.

PFS is defined as the time from the date of the first dose of study drug to the date of first documentation of objective tumor progression or death due to any cause, whichever occurs first. Subjects who die without a reported progression will be considered to have progressed on the date of their death. Subjects who did not progress or die will be censored on the date of their last tumor assessment. Subjects who did not have any on-study tumor assessments and did not die will be censored on their date of enrollment/randomization (as applicable). Subjects who started anti-cancer therapy without a prior reported progression will be censored on the date of their last tumor assessment prior to the initiation of subsequent anti-cancer therapy.

OS is defined as the time from the date of the first dose of study drug to the date of death due to any cause. All deaths will be included in the analysis.

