- TEAEs leading to death related to CX-2009
- TEAEs of Special Interest by maximum severity grade
- TEAEs of Ocular Toxicity related to CX-2009 by maximum severity grade
- TEAEs of Neuropathy related to CX-2009 by maximum severity grade
- TEAEs of Hepatic Disorders related to CX-2009 by maximum severity grade
- TESAEs
- Grade 3 or higher TESAEs
- Grade 3 or higher TESAEs related to CX-2009

Each subject will be counted only once within each level of the summary (PT or SOC). If a subject experiences more than one TEAE within a PT or SOC, only the TEAE with the strongest relationship or the maximum severity, as appropriate, will be included in the summaries of relationship and severity.

The above list of summary tables will also be produced by MedDRA PT (based on descending frequency of the total column) by dose level or by cancer type.

The TEAE summary tables by SOC and PT will be provided upon request to the DSMB.

TEAE profile summaries will also be created for infusion reactions. This table will summarize the frequency of events, time from event onset to the start time of the first infusion (hours), time from the event onset to the start time of the most recent infusion (hours), duration of the event (hours), duration category (<1 hour, 1 to 6 hours, >6 hours), severity grade, outcome, action taken, and other action taken with medication.

Profile summaries will also be created for TEAEs of Ocular Toxicity, TEAEs of Neuropathy, and TEAEs of Hepatic Disorders. These tables will summarize the time from event onset to the start time of the first infusion (days), duration of the event (days), duration category (<=7 days, 7 to 14 days, >14 days), severity grade, outcome, action taken, and other action taken with medication.

A tabular summary of deaths by study period (Screening, Treatment, Follow-Up) will be provided by dose level and by cancer type.

No inferential statistical tests will be performed for safety analyses.

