| Subjects who started anti-cancer therapy without a prior reported progression | Date of their last tumor assessment with a response assessment other than not evaluable prior to the initiation of subsequent anti-cancer therapy | Censored |
| Died or progressed (on treatment*) after a missed assessment | Date of death or disease progression | Progressed |
| Died or progressed in follow-up | Date of last tumor assessment with a response assessment other than not evaluable | Censored |

* Subjects who discontinued the study 30 or fewer days from the last dose of study drug are considered to have discontinued the study during the treatment period. Subjects who discontinue the study more than 30 days after the last dose of study drug are considered to have discontinued the study while in follow-up.

OS

OS is defined as the time from the date of the first dose of study drug to the date of death due to any cause (as captured on the Study Discontinuation, Treatment Termination, Substudy Discontinuation, Survival Status and/or AE CRF pages). Two analyses of OS will be conducted. The first will analyze all on-treatment deaths (deaths occurring within 30 days of last dose of study drug) while the second will analyze all on-study deaths (deaths occurring after first dose of study drug while on study). Subjects who are last known to be alive and/or lost to follow-up are censored at the date of last contact (as captured on the Discontinuation Call, Study Discontinuation, Treatment Termination, Survival Status, and/or Substudy Discontinuation CRF pages). Interim analyses of OS would use the data cut date as the censoring date of last contact if the subject is last known to be alive and/or lost to follow-up. OS is calculated for using the SP.

Table 4. Date of Censoring

| Description of Situation | Date of Progression or Censoring | Outcome |
|---|----------------------------------|----------|
| Last known to be alive and/or lost to follow-up | Date of last contact | Censored |

Please note that the scan date of the tumor assessment associated with the reported response assessment will be used as the tumor response date referenced above (i.e., first documentation of objective tumor response, first documentation of objective disease progression, and first documentation of objective tumor progression).

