Estimates of time-to-event endpoints (DOR, TTR, PFS, and OS) will be obtained using the Kaplan-Meier method. Kaplan-Meier curves will be provided for these endpoints. A swim lane plot will be provided for DOR. DOR and TTR will also be summarized using descriptive statistics for confirmed objective responders.

The median, and 95% CIs around the DOR, TTR, PFS, and OS will also be calculated using the Kaplan-Meier method. The range of TTR, PFS and OS will be provided as well. Frequencies and percentages will be summarized for event rates and censored observations of the time-to-event endpoints. Six- and twelve-month and 2-year survival rates will be included as well. The number and percentage of disease progressions and deaths will be included (replacing the event rate) in the PFS summary.

CBR16 and CBR24

Breast cancer patients will also have CBR16 and CBR24 summarized by dose level and also by cancer subtype (TNBC, HR+/HER2-, HER2+). CBR16 is defined as the proportion of subjects with best overall response of CR or PR or with SD for at least 16 weeks. CBR24 is defined as the proportion of subjects with best overall response of CR or PR or with SD for at least 24 weeks. CBR16 and CBR24 will only be calculated for subjects in the REP.

SD Duration is defined as the time interval from the start of the treatment to the date of subsequent PD or on-treatment death. In the absence of PD or on-treatment death before the analysis cut-off date, it is the time from the start of treatment to the date of the last adequate tumor assessment before the cut-off date.

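### The SAP plans two unranked OS analyses; the first counts only deaths within 30 days of the last dose, has no censoring rule for later deaths, and does not estimate OS as defined

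*SAP*

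**What the plan says.** SAP section 13.1.2 sets the endpoint: "OS is defined as the time from the date of the first dose of study drug to the date of death due to any cause". The same paragraph then announces two analyses. For one, "The first will analyze all on-treatment deaths (deaths occurring within 30 days of last dose of study drug"). For the other, "the second will analyze all on-study deaths (deaths occurring after first dose of study drug while on study"). Neither is called main or supportive.

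The only OS censoring rule, in the text and in Table 4, covers subjects "last known to be alive and/or lost to follow-up", who are censored at last contact (or at the data cut in an interim analysis).

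OS is estimated by Kaplan-Meier in the safety population with a median and 95% CI, and "Six- and twelve-month and 2-year survival rates will be included as well".

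Three other places bear on this:

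- Core section 11.3 (Appendix A of the protocol) says of OS: "All deaths will be included in the analysis". Protocol section 9.2 says that where the two conflict, "the SAP supersedes the Core".
- SAP section 13.1.3 continues survival monitoring after progression, so later deaths are collected.
- SAP section 12.1 already plans a safety display: "A tabular summary of deaths by study period (Screening, Treatment, Follow-Up) will be provided".

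**The concern.** The event set of the first analysis does not match the endpoint defined at the head of its own paragraph. A subject who dies on day 31 or later after the last dose is not an event in that analysis, and is not last known to be alive either. No rule says what to do with that subject, so the programmer must choose, and the estimate depends on the choice.

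Subjects must stop treatment for progression, for a related adverse event that precludes further dosing, or for intercurrent illness (SAP section 4.5). The deaths removed are therefore likely to be those of subjects whose prognosis had just worsened.

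The SAP does not restrict the medians and landmark rates to one of the two analyses. Two sets of OS figures could exist with no pre-stated choice between them. SAP section 1 says the analyses may support SRC and DSMB review, publications and FDA submissions.

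**Working it through.** The documents state no OS median, survival rate or death count, so there is no planned figure to reproduce. The size has to be shown over assumed ranges.

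**Inputs from the documents**
- Median exposure 7.3 weeks, maximum 60 weeks, at the 30 November 2019 data lock (protocol section 1.3.4).
- Planned treatment of about 6 months on average, and study completion about 2 years after the last enrolment (SAP section 4.3).
- Expected survival of at least 3 months at entry (protocol section 4.1).
- 99 treated subjects: 37 + 39 + 10 + 3 + 10 = 99 (SAP section 4.2).

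**Step 1. How long a subject can be an event in the first analysis (no model needed)**
- At the median exposure: (7.3 × 7 + 30) / 30.4375 = 81.1 / 30.4375 = 2.7 months.
- At the maximum exposure: (60 × 7 + 30) / 30.4375 = 450 / 30.4375 = 14.8 months.

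On that data cut, about half the subjects could not be an event after month 2.7, and none after month 14.8. Exposure of subjects still on treatment at the cut could extend this. Without such an extension, a 2-year rate from the first analysis holds no information beyond about month 15.

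**Step 2. Share of deaths left out**

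Assume exponential survival with rate λ = ln 2 / (OS median), exponential time on treatment with median 7.3 weeks (rate μ = 0.413 per month), the two independent, and 24 months of follow-up. With d = 30 / 30.4375 = 0.986 months:

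share left out ≈ [e^(−λd) · μ/(μ+λ) − e^(−24λ)] / [1 − e^(−24λ)]

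| Assumed OS median | e^(−λd) | μ/(μ+λ) | e^(−24λ) | Left out |
|---|---|---|---|---|
| 6 months | 0.892 | 0.781 | 0.063 | 68% |
| 9 months | 0.927 | 0.843 | 0.158 | 74% |
| 12 months | 0.945 | 0.877 | 0.250 | 77% |
| 15 months | 0.955 | 0.899 | 0.330 | 79% |

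Simulation (400,000 subjects per scenario) gives the same four figures. With treatment time and survival positively correlated (Gaussian copula, 0.6), the shares are 74%, 82%, 85% and 87%. At a 3-month OS median the formula gives 51%. With a 26-week treatment median, close to the planned 6 months, simulation gives 38–65%.

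Death truncates treatment in the model, so the realised median exposure was 5.7–7.2 weeks in the 7.3-week scenarios, slightly below the reported value.

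**Step 3. Effect on 12-month OS at 7.3 weeks' exposure**

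Rule (a) censors a later death at its date or last contact, the nearest reading of Table 4. Rule (b) censors at last dose + 30 days, which the SAP does not state. Ranges run from independent to correlated.

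| Assumed OS median | True | Rule (a) | Rule (b) |
|---|---|---|---|
| 6 months | 25% | 68–74% | 25–55% |
| 9 months | 40% | 77–84% | 39–73% |
| 12 months | 50% | 82–89% | 51–81% |
| 15 months | 57% | 86–91% | 58–86% |

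Rule (a) raised the curve in all 16 scenarios (two exposures, four OS medians, with and without correlation). At 7.3 weeks its median was never reached. Rule (b) was essentially unbiased under independence and too high under correlation.

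**Step 4. A second model**

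Here the hazard changes when treatment stops: 1–3% per month on treatment, then a median of 4–10 months after stopping, with 12–30 months of follow-up and 7.3 weeks' median exposure. Between 12% and 23% of deaths count. True 12-month OS of 19–51% becomes 75–91% under rule (a) and 41–71% under rule (b). Together with the 13–32% counted in step 2 (100% minus 68–87%), this gives 12–32%.

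**The case against.** The strongest reply is that a sound OS estimate is already in the plan. The second analysis counts all on-study deaths, takes them from the survival-status form among others, and uses the follow-up after progression. This stands, and it limits the harm.

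Four stronger readings are tempting and are not supported:

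- **The first analysis takes precedence because it is listed first.** Sentence order is not a ranking, and the SAP ranks neither. How the two outputs would be titled is also not stated.
- **There is an unresolved conflict with the Core.** Protocol section 9.2 settles it in the SAP's favour. What remains is the mismatch inside the SAP paragraph.
- **It is a fact that most deaths are dropped.** No death counts are given. The 7.3 weeks comes from a data cut at which some subjects may still have been on treatment, and at the planned exposure some scenarios leave out fewer than half.
- **The bias arises whatever the censoring date.** Censoring at last dose + 30 days is essentially unbiased if treatment time and survival are independent. Mandatory stopping for progression makes independence unlikely, but the strength of the link is assumed.

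It is also fair that OS is a secondary, descriptive endpoint in an open-label study stopped at 99 subjects. Objective response rate is the primary efficacy endpoint, and no OS test or OS-based decision rule is stated.

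**Conclusion.** The point holds as a moderate defect that should be fixed. The first analysis does not estimate OS as the SAP defines it, and it cannot be programmed without inventing a censoring rule. These two statements follow from the text alone.

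The direction of the error is upward under last-contact censoring. It is also upward under last dose + 30 days when stopping is linked to prognosis, which is likely here.

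The size is conditional. The range of 12–32% of deaths counted rests on 7.3 weeks' median exposure, exponential times and the assumed survival ranges (OS medians of 6–15 months in the first model). About half of deaths would count at a 3-month OS median, and 35–62% with a 26-week treatment median.

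A reader might infer that the trial would lack a valid OS result or that its main conclusions are at risk. The documents do not support that, because the all-deaths analysis is planned and OS is secondary.

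**What to change.** In SAP section 13.1.2, name the analysis of all deaths from any cause after first dose, in the safety population, as the only OS analysis. State that the Kaplan-Meier median and the 6-, 12- and 24-month rates come from it.

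Delete the on-treatment OS analysis and report deaths within 30 days of last dose as n (%) in the death table of SAP section 12.1. If the sponsor wishes to keep it, label it a supportive on-treatment mortality summary, not OS, and add a row to Table 4 giving the censoring date for subjects who die after the window.

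The cost is a sentence or two in the SAP and, if the analysis is deleted, one fewer supportive output. No new data are needed.

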1.3.4 Summary of CX-2009 Clinical Experience

Clinical data from Module CTMX-M-2009-001 as of a 30 November 2019 data lock point are summarized below.

Median duration of exposure to CX-2009 as of the data lock point was 7.3 weeks (maximum 60 weeks).

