| q 21 days | every 21 days |
| RECIST | Response Evaluation Criteria in Solid Tumors |

| Abbreviation | Definition |
|---------------------|---|
| REP | response evaluable population |
| RP2D | recommended Phase 2 dose |
| SAE | serious adverse event |
| SAP | statistical analysis plan |
| SD | standard deviation |
| SD | stable disease |
| SOC | system organ class |
| SP | safety population |
| SRC | safety review committee |
| TEAE | treatment-emergent adverse event |
| TESAE | treatment-emergent serious adverse event |
| TMTB | total measured tumor burden |
| TTR | time to response |
| WHODrug | World Health Organization Drug Dictionary |

1. Purpose

This Statistical Analysis Plan (SAP) describes the statistical methodology and data handling for CytomX Therapeutics, Inc. protocol module number CTMX-M-2009-001 (A Phase 1-2, Open-Label, Dose-Finding, Proof of Concept, First-in-Human Study to Evaluate the Safety, Tolerability, Pharmacokinetics, and Pharmacodynamics of CX-2009 in Adults with Metastatic or Locally Advanced Unresectable Solid Tumors). The analysis specified in this SAP will be used to support safety review committee (SRC) and data and safety monitoring board (DSMB) analyses, publications, and FDA submissions. The proposed analyses may not be carried out if the sample size is not adequate.

The ICH guideline E3 "Structure and Content of Clinical Study Reports" was used as a guide to the writing of the plan.

This SAP is based on the following study documents:

- Protocol Core Amendment 01, 11 November 2016
- Protocol Module Amendment 06, 09 August 2017,
- Protocol Substudy V1.0, 04 May 2018
- Annotated Case Report Forms

The enrollment in CTMX-M-2009-001 was stopped by sponsor decision as of 07 July 2020, with a final enrollment of XX subjects into Parts A, A2, B, and C1.

2. Study Population

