The EOT Visit will be conducted 30 days (± 7 days) after the last infusion of CX-2009. Once a subject experiences progressive disease, they will continue to be monitored for survival. All subjects will return for Follow-Up Visits every 3 months after the EOT Visit for 1 year and then every 6 months to ensure resolution of toxicities and as applicable, confirm negative pregnancy status. During the EOT Visit, subjects will be followed for resolution of toxicity. Women of childbearing potential will undergo monthly pregnancy testing while on study drug and through 50 days after the last dose of CX-2009, or 6 months after the last dose of CX-072, as applicable, whichever is later. Thereafter, Follow-Up Visits will be conducted for survival information and may be performed by telephone.

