7.1 Interim Analyses

No formal interim analysis is planned.

Administrative interim analyses on safety and efficacy or on PK, immunogenicity, and selected biomarkers may be performed several times prior to completion of the study in order to facilitate program decisions and to support study presentations or publications.

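### At an interim cut, the SAP censors OS for subjects lost to follow-up at the data cut date, so time nobody observed is counted as survival

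*SAP*

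**What the plan says.** The general OS rule in SAP 13.1.2 censors subjects who are alive or lost at the date of last contact, taken from named CRF pages. Table 4 has a single row: "Last known to be alive and/or lost to follow-up | Date of last contact | Censored".

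The next sentence of the text departs from this for interim analyses, which "would use the data cut date as the censoring date of last contact if the subject is last known to be alive and/or lost". Loss here means loss to follow-up. Table 4 has no matching interim row.

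On follow-up, SAP 4.3 states: "All subjects will return for Follow-Up Visits every 3 months after the EOT Visit for 1 year and then every 6 months", and later that "Follow-Up Visits will be conducted for survival information and may be performed by telephone".

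On use, SAP 7.1 plans no formal interim analysis, but administrative looks at efficacy "may be performed several times prior to completion of the study in order to facilitate program decisions and to support study presentations or publications". SAP section 1 says the analyses in the plan "will be used to support safety review committee (SRC) and data and safety monitoring board (DSMB) analyses, publications, and FDA submissions".

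OS is estimated by Kaplan-Meier, with median, 95% CI and 6-month, 12-month and 2-year rates. Two versions are planned. "The first will analyze all on-treatment deaths (deaths occurring within 30 days of last dose of study drug"); the second covers all on-study deaths.

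**The concern.** Kaplan-Meier needs each subject to be at risk only while a death would be seen. A lost subject moved forward to the cut stays in the denominator while their death cannot enter the numerator. The sentence names exactly the group for whom survival to the cut is unknown.

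The plan's other censoring rules do not extend follow-up this way. PFS and DOR stop at the last tumour assessment, and stable-disease duration before a cut-off stops at the last adequate assessment.

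Off-treatment contacts are 3 and then 6 months apart, so unconfirmed status at a cut is to be expected unless someone checks. A programmer following Table 4 and one following the text would also produce different interim curves.

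At stake is an interim survival figure that may be presented or used for programme decisions. The study is single-arm, so no control curve carries the same error.

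A smaller point, with no bias claimed: the analysis limited to deaths within 30 days of last dose is called OS although OS is defined by death from any cause, and no censoring date is given for subjects who die later.

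**Working it through.** **Inputs.** From the documents: the two censoring rules, the Kaplan-Meier estimator, the contact spacing, 99 treated subjects (SAP 4.2), and from Protocol 1.3.4 "Median duration of exposure to CX-2009 as of the data lock point was 7.3 weeks (maximum 60 weeks"). The documents contain no OS estimate or loss rate, so there is no figure of the plan's own to reproduce. Assumed: exponential OS with median 6, 9 or 12 months; cut uniform from 6 to 24 months after first dose; exponential loss independent of prognosis, set so that 0, 5, 10 or 20% of subjects are lost before death and before the cut.

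**Step 1: direction, in ten invented subjects.** Deaths at 2, 5, 6, 9, 11 and 14 months; last contacts of the rest at 4, 8, 12 and 15; cut at 18.
- Last-contact rule: 9/10 × 7/8 × 6/7 = 0.675 at 6 months; × 4/5 × 3/4 = 0.405 at 12 months.
- Data-cut rule: nobody leaves the risk set before 18 months, so 7/10 = 0.700 and 5/10 = 0.500.

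**Step 2: size with deaths reported promptly.** Let λ = ln 2 / median be the death rate and μ the loss rate. Under the data-cut rule a death is recorded only if it precedes loss, so the curve tends to

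S(t) = 1 − [λ/(λ+μ)] × [1 − exp(−(λ+μ)t)].

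Worked case, median 9 months and 10% lost: λ = 0.0770 and μ = 0.0126 per month, sum 0.0896. exp(−12 × 0.0896) = 0.341; 1 − 0.341 = 0.659; × 0.859 = 0.566; S(12) = 0.434. Truth is 0.5^(12/9) = 0.397, so the excess is 3.7 points.

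Simulation (400,000 subjects per scenario) agrees with the formula to within 0.2 points:

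| Lost | 12-month OS, data-cut rule (median 6 / 9 / 12) | Excess over 0.250 / 0.397 / 0.500, points |
|---|---|---|
| 0% | 0.250 / 0.398 / 0.500 | 0 |
| 5% | 0.276 / 0.417 / 0.514 | 1.4-2.6 |
| 10% | 0.302 / 0.435 / 0.528 | 2.8-5.2 |
| 20% | 0.358 / 0.475 / 0.558 | 5.8-10.8 |

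A second simulation, with 24-month uniform accrual, a cut 6 months after last enrolment and 3-26% of subjects lost, gave about 1 to 9 points at 12 months and 3 to 18 points at 24 months. The 2-year rate is hit harder.

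**Step 3: deaths learned only at the next scheduled contact.** The contact grid is every 21 days on treatment (exponential time to stopping, median set to 7.3 weeks), a visit 30 days after last dose, then 3-monthly for a year and 6-monthly after. The data-cut excess at 12 months becomes 2.1-2.4, 3.4-4.8, 4.8-7.4 and 7.6-12.7 points at 0, 5, 10 and 20% loss. Even with nobody lost, the rule is then no longer unbiased.

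**Step 4: the alternatives.**
- Last contact on the grid, no status update, deaths prompt: 0.232 / 0.378 / 0.480 at 0% loss and 0.218 / 0.366 / 0.470 at 20%, that is 1.8-3.2 points low. Deaths between contacts are counted but survivors' time since last contact is not.
- Last date known alive, with status updated at the cut: no bias at 0% loss, and 0.1-1.3 points low at 5-20%.

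**Step 5: precision.** At n = 99 the simulated 95% half-width for 12-month OS is 9.4-10.7 points.

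**The case against.** **Reach.** The strongest reply is that this hardly matters. The interim looks are optional, enrolment had already stopped, planned outputs follow database lock, and OS is secondary with no decision rule. SAP 7.1.1 gives the SRC safety data, and the DSMB tables named in SAP 7.1.2 do not include OS, so the general statement of purpose does not show that either body would see interim OS. All of this stands and limits the reach.

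**Size.** The loss rates are assumed, and the 20% column has no support in the documents. SAP 10.1 tabulates by dose level and cancer type, where precision is far worse than at n = 99. Protocol 1.3.4.1 reports 22 subjects at 8 mg/kg and 9 at 7 mg/kg. At 40% survival the binomial half-width is 1.96 × √(0.24/22) = 20 points and 1.96 × √(0.24/9) = 32 points. This stands too, but the error runs in one direction, is avoidable, and is not reflected in a confidence interval.

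**Remedy.** At 5% loss with prompt reporting, the plan's rule (1.4-2.6 points high) is about as far off as plain last-contact censoring (about 2.2 points low). A bare switch would gain little, so the status update has to be part of the fix.

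**Intent.** The sentence may have been meant only to cap contacts dated after the cut. Its words do not say that; they set the cut date for lost subjects too. Table 4 can be read as the general rule with the exception in the text above it, which makes the missing row a gap in presentation, but the exception itself remains wrong for lost subjects.

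**Conclusion.** The concern holds. As written, the interim rule treats subjects of unknown status as survivors to the cut and biases interim OS upward whenever anyone is lost or a death before the cut is not yet known. The wording and the direction are certain. The size is illustrative, resting on exponential OS with a median of 6-12 months and loss unrelated to prognosis. At 5-10% loss the 12-month bias lies within sampling error for 99 subjects; only near 20% does it approach it. The fault is not the use of a cut date as such, which is unbiased when survival to the cut is confirmed, but its use without that confirmation. It should be corrected before any interim OS is produced. It does not threaten the final analysis of all on-study deaths.

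**What to change.** Replace the interim sentence in SAP 13.1.2 with:

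> In every OS analysis, interim or final, subjects not known to have died on or before the data cut are censored at the last date known alive on or before the cut; the cut date itself is used only for subjects whose survival was confirmed on or after it.

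Align Table 4 with this text, and require survival status to be updated at each cut. Separately, label the 30-day analysis as on-treatment mortality and state the censoring date for subjects who die later.

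The drafting cost is one sentence, one table row and one label, and last-contact dates are already on the CRF. The real cost is the site work of a status check at each interim cut, some of it outside the 3- and 6-month contacts, though telephone contact is already allowed. Interim OS may read somewhat lower as a result.
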